## Respiratory symptomatic

Any participant presenting with cough or phlegm of duration of more than 14 days.

## TB case:

A participant in whom TB has been confirmed bacteriologically, or a participant who started treatment empirically and showed response to treatment after the initial phase of TB treatment, as documented by the PNCT.

## TB Case Classification

- A bacteriologically confirmed case of pulmonary TB is defined by either GeneXpert® OR mycobacterial culture (MGIT™) positive for *M. tuberculosis complex*
- 2. A bacteriologically unconfirmed case is defined by:
  - 1. Not meeting definition for bacteriologically defined case
  - Decision by the PNCT of the necessity for empiric treatment with anti-TB chemotherapy

A TB case is categorized by anatomical site of disease:

- 3. Pulmonary TB (PTB): The disease affects the lung parenchyma. Pulmonary TB is the most common form.
- 4. Extrapulmonary TB (EPTB): The disease affects other sites including lymph nodes, pleurae, meningeal, pericardial, peritoneal, spinal, intestinal, genitourinary, larynx, spine, bones and joints, and skin.
- 5. A patient diagnosed with both pulmonary and extrapulmonary localisations of TB is classified as PTB + EPTB.

Classification based on history of Previous Treatment (in accordance with Paraguayan National TB guidelines):

Cases will be defined to whether or not the participant has previously received TB treatment.

- New treatment: A participant who has never had treatment for TB or who has taken anti-TB medicines (for treatment of active TB) for less than one month at time of enrolment.
- Current treatment: A participant who is currently taking anti-TB medicines (for treatment of active TB) for one month or more at time of enrolment.
- Previous treatment: further classified according to result of last treatment:
  - Relapse: A participant previously treated for TB, who has been declared cured or has completed treatment up to the final stage of treatment and currently diagnosed with a new episode of active TB, whether a reactivation or new episode of TB (re-infection)
  - Failure: A participant who has treatment failure at the end of his/her most recent treatment.
  - Lost to follow up: A participant declared lost to follow-up during his/her most recent treatment.
  - Other previously treated participants: All participants who have been previously treated but with unknown or undocumented treatment outcome of the most recent treatment.
  - Unknown history of previous treatment: participants who relate having been treated but without documentation, only verbal reference.

Classification based on patterns of drug resistance:

 Monoresistant, polyresistant, MDR, XDR TB (in accordance with Paraguayan National TB guidelines)

Classification based on HIV status

- Case of TB with HIV
- Case of TB without HIV
- Case of TB with unknown HIV status

Bacillary load and Severity of TB:

Bacillary load, as determined by:

- GeneXpert® cycle time (Ct) value
- MGIT™ culture time-to-positivity

Radiological severity

- CAD4TB score
- Unilateral, bilateral, pleural, miliary

- Presence of cavitations
- Percentage of lung affected as defined by a posteroanterior X-ray projection (<33%, 33-66%, >66%)
- Clinical severity (TBscore, Wejse et al. 2008 and TBscoreII, Rudolf 2014) Severity according to TBscore 2008: Class I (0-5 points)
- Class II (6-7 points)
- Class III (8 or more points)

Parameter	Points assigned TBscore	Points assigned TBscorell
Self-reported:		
Cough	1	1
Haemoptysis	1	-
Dyspnea	1	1
Chest pain	1	1
Night sweating	1	-
Anaemic conjunctivae	1	1
Tachycardia (>90/min)	1	-
Positive finding at lung aus-	1	-
cultation		
Axillary temperature >37.0	1	-
BMI <18	1	1
BMI <16	1	1
MUAC <220	1	1
MUAC <200	1	1

BMI: Body Mass Index; MUAC: Middle Upper Arm Circumference.

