strains identified with Whole Genome Sequencing. Nature and extent of the burden and risks associated with participation, benefit and group relatedness:

Individual burden: all participants will perform one visit with a medical doctor for medical history, physical exam, digital X-ray (with CAD4TB®) and AeoNose sampling. Participants will be offered voluntary HIV testing and counseling. In case of presumptive TB (estimated 20-30% of participants) two sputum samples will be taken, either spontaneous or saline-induced. One sample is tested with GeneXpert and the other with liquid mycobacterial culture. Cases of presumptive TB with both negative GeneXpert® and culture results will be followed-up after three and six months for repeat testing.

Individual and group health benefit: all participants will have a medical consultation and CXR. In case of an alternative diagnosis, the prison health service will be notified. People diagnosed in the study with active TB will be notified and referred to receive treatment through the PNCT according to national guidelines. All participants will eventually benefit from less exposure to infectious TB cases through optimized infection control measures and treatment of infected individuals. The study will provide the PNCT with epidemiological data of this vulnerable group to optimize future TB control strategies.

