## 3. STUDY DESIGN

Diagnostic prospective cohort study: mass screening through conventional symptoms screening by a doctor, a physical exam and with testing of CAD4TB® and AeoNose™ as well as bacteriological testing of presumptive cases.

An estimated 5000 individuals will be invited to participate. All prisoners and employees will be eligible for inclusion. The sample size is based on an estimated incidence of 3000-5000/100.000 and a presumptive number of 150-250 active TB cases to be found in order to have enough cases to first train the neural network (with at least 500 - 1000 healthy individuals and a 100 active TB cases) and then perform the blind predictions on the rest of the participants to establish sensitivity and specificity of the AeoNose™.

The study consists of one primary visit and, in case of suspicion of presumptive TB but no confirmed TB or alternative diagnosis, two follow-up visits after three and six months respectively. The estimated total study duration will be from February 2020 to May 2021. The study settingwill be the Buen Pastor, Esperanza and Tacumbú prisons in Asunción, Paraguay Required condition to perform the study in each of these three institutions is safety for the study team and also the guards and prisoners. In case of unstable conditions we will look for an alternative penal institution.

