#### Follow-up of presumptive TB cases

Participants who are considered presumptive cases of TB at Visit 1, but with negative sputum results or unable to produce sputum, will be followed-up after three and six months.

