#### Visit 2 and 3 (at three and six months after Visit 1)

Study procedures are the same as Visit 1 steps 1 through 5. Participants will be asked for symptoms, have a physical exam, undergo CXR with CAD4TB® and AeoNose™ breath sampling. At visit 2 and 3, all participants will be asked to produce two sputum samples. In case of positive results for *Mycobacterium tuberculosis*, confirmed cases will be notified to

the PNCT. After visits 2 and 3 a decision will be made by the study team on the final health status of the participant (either considered healthy or a TB case). In case of a high suspicion of TB the prison health authorities and the PNCT may decide to treat this individual for active TB. The result of this anti-tuberculosis treatment will be communicated with the study team.

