## AND / OR

Any participant with CAD4TB output score above the threshold level (to be determined), or presenting with CXR abnormalities as judged compatible with TB by the study doctor.

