#### 8.1 Primary study parameter(s)

Primary study parameters are the number of TB cases cases by CAD4TB® CXR analysis and AeoNose™ breath sampling.

A binary assessment of the presence or absence of illness has four possible outcomes: true positives (TP), false positives (FP), true negatives (TN) and false negatives (FN). The relationship of the four outcomes is the basis of sensitivity and specificity analysis which determines the accuracy and predictive value of a diagnostic tool.

*True positive:* A positive test result in a confirmed TB case.

*False positive*: A positive test result with negative sputum results and no confirmed TB during follow-up.

*True negative*: A negative test result with no confirmed TB during follow-up. *False negative*: A negative test result with confirmed TB during follow-up.

Receiver operating characteristics (ROC) will be generated using an ROC package, and bootstrapping to generate confidence intervals in the ROC plot. T-testing or McNemar's test will be used to compute P values when comparing the sensitivity of conventional screening and CAD4TB® and AeoNose™ at assumed levels of specificity. We will also use multivariate analysis to analyse influences of different combinations of participant characteristics.

CAD4TB®: The collection of digital CXR images will be analysed and compared to presumptive and confirmed cases. The number of true/false positives and negatives will be used to calculate sensitivity and specificity as described above. The predictive value of the test will be analysed.

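### A single positive among up to six sputum tests confirms a case, and because CAD4TB helps choose who is tested, the resulting false cases can tilt the section 8.1 sensitivity comparison against AeoNose

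*Protocol*

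**What the plan says.** - **Case rule.** Under TB Case Classification (section 6.1.1), a bacteriologically confirmed case "of pulmonary TB is defined by either GeneXpert" or MGIT culture. One positive is enough, and no repeat or agreeing result is required.
- **Tests per visit.** The Summary states: "One sample is tested with GeneXpert and the other with liquid mycobacterial culture".
- **Retesting.** Section 3 says that presumptive participants at visit 1 "but with negative sputum results or unable to produce sputum, will be followed-up after three and six months". The design paragraph of section 3 limits this to those with neither confirmed TB nor an alternative diagnosis. For the later visits: "At visit 2 and 3, all participants will be asked to produce two sputum samples". The maximum is therefore 2 tests x 3 visits = 6.
- **Who is tested.** Only presumptive participants give sputum at visit 1. One route to presumptive status is: "Any participant with CAD4TB output score above the threshold level (to be determined"). Others are symptoms or signs, or a chest film that the study doctor judges compatible with TB. An AeoNose result is not a route.
- **Use in the analysis.** Section 8.1 defines a true positive as: "A positive test result in a confirmed TB case". A false negative is a negative index test with TB confirmed during follow-up. The section plans P values comparing the sensitivity of conventional screening, CAD4TB and AeoNose.
- **Final status.** The study team decides it after visits 2 and 3, but no rule is given for setting aside a lone positive.

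**The concern.** An either-positive rule applied over several visits adds up the false-positive chances of each test. Most people tested do not have TB, so even very specific tests can add a visible number of false cases.

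These errors need not be shared equally by the two devices. False cases can arise only among people sent for sputum, and that group is enriched for CAD4TB positives. AeoNose plays no part in choosing them, so it is positive in them only at its own false-positive rate. In 8.1 such people would tend to count as CAD4TB true positives and AeoNose false negatives, so the error need not cancel in the planned comparison.

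False cases would also inflate the first main endpoint (section 6.1.2, number of TB cases). They would put some non-TB breath profiles among the TB cases used to calibrate the AeoNose network.

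**Working it through.** **Inputs from the protocol**
- Section 3: "An estimated 5000 individuals will be invited to participate", at 3000-5000 per 100,000. The protocol's own figure reproduces: 5000 x 3% = 150 and 5000 x 5% = 250 cases.
- Summary: "In case of presumptive TB (estimated 20-30% of participants) two sputum samples will be taken".
- AeoNose sensitivity/specificity (section 5.2): 88%/92% in the Paraguay pilot; 78-85%/42-55% in Indonesian patients with suspected TB.
- CAD4TB sensitivity/specificity (section 1): 95%/70%, depending on the threshold.

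**Assumptions, not in the protocol**
- Specificity sp of each sputum test, taken as equal for GeneXpert and culture, with independent errors.
- Share c of false cases that are CAD4TB-positive.
- For illustration, an AeoNose false-positive rate q of 20% in those tested. The Paraguay pilot implies 8%, the Indonesian study 45-58%.

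**Step 1: base case.** Midpoints are 4% TB and 25% presumptive. True cases T = 5000 x 0.04 = 200. Presumptive without TB, N = 5000 x 0.25 - 200 = 1050. This treats all 5000 invited as participants and all true cases as presumptive. At the 72% average consent among prisoners cited in section 4.3, T = 144 and N = 756, and the shares below do not change.

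**Step 2: false cases, upper bound.** F = N x (1 - sp^6); share s = F/(T + F).

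**Step 3: loss of observed sensitivity.** Observed sensitivity = (T x Se + F x r)/(T + F), where r is the chance that the device is positive in a false case (q for AeoNose, c for CAD4TB). The loss is therefore s x (Se - r).

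| sp | 1 - sp^6 | F | s | AeoNose loss (Se 88%, q 20%) | CAD4TB loss (Se 95%, c 0.9) | CAD4TB loss (c 0.7) |
|---|---|---|---|---|---|---|
| 99.9% | 0.60% | 6.3 | 3.0% | 2.1 points | 0.2 | 0.8 |
| 99.5% | 2.96% | 31.1 | 13.5% | 9.2 | 0.7 | 3.4 |
| 99% | 5.85% | 61.4 | 23.5% | 16.0 | 1.2 | 5.9 |

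Example at 99.5%: 0.1346 x (88 - 20) = 9.2 points; 0.1346 x (95 - 70) = 3.4 points.

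The corners are T = 250 with N = 750 (5% TB, 20% presumptive) and T = 150 with N = 1350 (3% TB, 30% presumptive). Between them, F is 4-8 at 99.9% and 22-40 at 99.5%, with an AeoNose loss of 1.2-3.5 and 5.6-14.3 points.

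**Step 4: how firm is the direction?** The losses are equal when c = 0.95 - (Se - q), Se being AeoNose sensitivity.
- Se 88%, q 20%: c = 0.27.
- 88%/92%: c = 0.15.
- 85%/55%: c = 0.55.
- 78%/42%: c = 0.75.

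At sp = 99%, 78%/42% gives an AeoNose loss of 0.235 x (78 - 58) = 4.7 points. CAD4TB loses 5.9 points at c = 0.7, so the gap reverses.

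At 70% CAD4TB specificity, 4800 x 0.30 = 1440 people without TB would be CAD4TB-positive, more than the 1050 presumptive, so that figure points to a high c. At 90% specificity, 480/1050 = 0.46 would be CAD4TB-positive by that route.

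**Step 5: fewer than six tests.** If 60% are retested and the rest have two tests, F at 99% is 1050 x (0.6 x 5.85% + 0.4 x 1.99%) = 45. The share is 18% and the AeoNose loss 12.5 points.

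**Step 6: what stricter references leave, at 99.5%.**
- Culture-positive only: 1 - 0.995^3 = 1.49%, or 15.7 false cases, about half of 31.
- Both tests positive at the same visit: 1 - (1 - 0.005^2)^3 = 0.0075%, or 0.08 false cases.

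**The case against.** - **Size.** A reader might infer that false cases lower AeoNose sensitivity much more than CAD4TB sensitivity. The documents do not support that without conditions. They give no specificity for either sputum test and leave the CAD4TB threshold open, and symptoms alone can also lead to testing. Their suspected-TB figures for AeoNose imply 45-58% false positives. At 99.9% specificity the effect is about 2 points, and with 78%/42% and c below 0.75 it reverses. This objection stands.
- **Six tests for everyone.** This too is only an upper bound. People with an alternative diagnosis are not retested, some cannot produce sputum, and follow-up will be incomplete. If errors repeat within a person, 1 - sp^6 is too high. This stands.
- **A culture-based reference is no full protection.** If culture errs as often as GeneXpert, about half the false cases remain. If culture is close to perfect, only three of the six tests can err and the problem is roughly half as large from the start. This stands, and is why a second, both-positive reference is needed.
- **The root cause is who gets tested.** A stricter reference does not change CAD4TB's part in selecting people for sputum. Any false cases that remain are just as enriched for CAD4TB positives. This stands, and the report should say so.
- **This belongs in the SAP.** Sensitivity analyses often do, and the either-positive rule is not wrong in itself. But the protocol itself fixes the rule, the retesting and the comparison, and together they create an error that can favour one device.

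**Conclusion.** The concern holds in a limited form. The text establishes the mechanism: one positive suffices, up to six tests are possible, and CAD4TB but not AeoNose leads to testing. False cases therefore tend to be CAD4TB-positive and can bias the 8.1 comparison against AeoNose.

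The text does not establish the size. In the base case, false cases range from about 3% of all cases at 99.9% specificity to 23.5% at 99%, as upper bounds. The matching AeoNose loss is about 2 to 16 points at a 20% false-positive rate. These figures rest on assumed specificity, independent errors, full retesting and an assumed AeoNose false-positive rate. The direction holds for most of the cited inputs but not all.

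This does not show that the either-positive rule should be dropped. It supports a cheap, pre-set check on a primary comparison.

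**What to change.** Keep the either-positive rule for the case count and the main analysis. In section 8.1, pre-specify that both devices' accuracy and the paired sensitivity comparison are repeated with:

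1. culture-positive cases only;
2. cases with GeneXpert and culture both positive at the same visit.

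In each repeat, leave confirmed cases that miss the stricter definition out of both the case and the non-case group. Tabulate single-positive cases by test, visit and previous-treatment class, all of which the study records.

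Report a device difference as robust only if its direction holds under these references. State that this does not remove the separate bias from CAD4TB helping to choose who is tested.

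Cost: a few lines in 8.1 and one table, with no change to study procedures. The strict analyses will have fewer cases, lose some true paucibacillary cases and give wider intervals.

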## 6.1.2 Main study parameter/endpoint

- 1. The total number of TB cases found by GeneXpert® and/ or culture of Mycobacterium tuberculosis complex.
- 2. Number of TB cases correctly identified by AeoNose™.
- 3. Number of TB cases correctly identified by digital X-ray with CAD4TB®.
- Factors affecting or influencing sensitivity and specificity of AeoNose™ and CAD4TB®, e.g. medication use, smoking and drugs, co-morbidities, BMI, dental status

#### 6.1.3 Secondary study parameters/endpoints

- Costs of different (theoretical) screening algorithms using AeoNose™, CAD4TB® or both in conjunction.
- 2. Signal differences and diagnostic performance of AeoNose™ and CAD4TB® in:
  - a. HIV cases (and CD4 count if available)
  - b. Patients with syphilis (and disease stage if available)
  - c. Diabetes cases (insulin dependent or non-insulin dependent)
  - d. Cases of EPTB
- 3. Number of incidental CXR findings and the effect on CAD4TB® output score.
- 4. Numbers of Mycobacterium tuberculosis complex bacterial strains identified.

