The digital CXR image will be analysed by CAD4TB® and the doctor will interprete the CAD4TB® output score and check the CXR for alternative diagnosis. All the findings by the study doctor will be recorded in the digital case record form. At the end of this visit the doctor will decide on health status of the participant: either the participant is considered healthy or a presumptive TB case.

For healthy participants the study ends after this 5th station.

- 6. Presumptive TB cases (see 6.1.1 Case definitions) will be asked to produce two sputum samples outside, preferably in the open air. Sputum can be either be produced spontaneously or via sputum induction with nebulized saline. Saline solution will be nebulized using a portable nebulizer. Sputum samples can deposited in standard containers. Samples will be stored in a cool box and transported to the laboratory the same day. Samples will then be processed and analysed by the National Reference Laboratory, Laboratory San Alfonso and IICS using GeneXpert® molecular testing and MGIT mycobacterial culture.
- 7. All participants will be educated about the importance of seeking medical care if symptoms compatible with TB emerge at any time.
- 8. In case a participant is passively identified with TB during the study period by the prison health services or PNCT, the study researchers will be notified. Clinical and microbiological data will be shared based on informed consent given by the participant.

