#### 5. INVESTIGATIONAL PRODUCT

#### 5.1 Name and description of investigational product(s)

- AeoNose™ (the eNose Company, Zutphen, the Netherlands):
- The Aeonose™ is a diagnostic device for exhaled-breath analysis. It is portable and requires a participant to breathe through the device for five minutes at tidal breathing.
  Volatile organic compounds (VOC) in the breath are captured by metal-oxide sensors. The unique 'smell print' of TB can be identified by an algorithm that is built on a de-blinded sample of the population in the calibration phase using an artificial neural network.
- CAD4TB® (Delft Imaging, Veenendaal, the Netherlands):

The CAD4TB® software analyses an X-ray image and detects the many different abnormal structures that may be related to TB. The system has been trained in the detection of these abnormalities by applying machine learning to thousands of healthy and diseased X-rays from over 15 countries, through which it has become accurate and reliable. The output of the CAD4TB® software is a score between 0 and 100, indicating the likelihood that the participant, above a threshold score, has possible, probable or definite (active) TB. The CAD4TB® software also outputs a 'heatmap' – a colour-coded image of the lungs indicating regions of abnormality.

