#### 6.1.4 Other study parameters

- Body weight (kilograms)
- Height (centimetres)
- Blood pressure and heart frequency
- Body temperature (axillary)
- Upper arm circumference
- Date of birth
- Place of birth
- Place of residence
- Gender (male/female)
- Sexual orientation
- Nationality
- Level of education (none, primary school, secondary school, vocational, higher education, unknown)
- Occupational history
- Civil state (single, married, widowed, separated, divorced, unknown)
- Ethnicity
  - If indigenous: specific indigenous ethnicity
- Dental state (good / plaque / inflamed gums / broken or missing teeth)
- Symptoms (including onset and intensity)
  - Cough
  - Sputum or haemoptysis
  - Weight loss

- Night sweats
- Chest pain
- Dyspnea
- Other
- Medical history and co-morbidities
- Previous diagnosis/treatment for TB (year and duration of treatment in months)
- Location in prison (cell, hallway, yard, others)
- Date of current prison entry, previous prison entries
- Medication (especially antibiotics)
- Smoking
- Drug use
- Factors influencing breath signal: intake and timing of ingestion of food, drinks, cigarettes
- CAD4TB® output score
- Radiological severity of TB
- AeoNose™ breath profiles
- GeneXpert® cycle time (if positive)
- MGIT™ culture time-to-positivity (if positive)
- Clinical severity of TB (TBscore, Wejse et al. 2008 and TBscorell, Rudolf 2014)
- CXR abnormalities as described by study doctor (infiltrate, cavity, lymphadenopathy, mass lesion, pleural abnormality, etc.)

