## Digital CXR and CAD4TB®:

X-ray image will be taken using a digital X-ray system connected with CAD4TB® software. Participants will be asked to stand in front of the panel while one posterioranterior X-ray image is taken. Images will be processed by the CAD4TB® software. A TB likelihood output score is presented to the doctor within minutes. Study doctors will also view and interprete the digital CXR during the consultation.

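### Incidental chest X-ray findings are recorded by a doctor who is given the CAD4TB score, so their association with that score (6.1.3 item 3) can be biased in either direction

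*Protocol*

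**What the plan says.** - **Endpoint.** Section 6.1.3 item 3 is the "Number of incidental CXR findings and the effect on CAD4TB" output score. The recorded finding is the explanatory variable and the score is the outcome.
- **Source of the findings.** Section 6.1.4 lists "CXR abnormalities as described by study doctor". No second reader or masked reader is named for this variable.
- **When the score exists.** In section 3, Visit 1, the film is taken and scored at station 3. The doctor sees the participant at station 5.
- **Who gets the score.** Section 6.2: "A TB likelihood output score is presented to the doctor within minutes". The next step there has the same person reading the film: "Study doctors will also view and interprete the digital CXR during the consultation".
- **How the two are combined.** Section 3, Visit 1, has the doctor interpret the CAD4TB "output score and check the CXR for alternative diagnosis" in one sentence, and then: "All the findings by the study doctor will be recorded in the digital case record form".
- **Labelling.** Section 6.1.1 lets the same doctor judge whether X-ray abnormalities are compatible with TB. The score itself also enters the presumptive-TB definition, through an "output score above the threshold level (to be determined").
- **Heatmap.** Section 5.1 says the software also produces "a colour-coded image of the lungs indicating regions of abnormality". It does not say that the doctor sees it.

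**The concern.** To learn whether non-TB pathology shifts the CAD4TB score, the pathology has to be ascertained independently of the score. Here the person who records it is handed the score and works with it while reading the film. Two things can then vary with the score:

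1. **Detection.** A high score may prompt a longer look, so more minor findings are recorded on high-score films.
2. **Labelling.** A high score may lead the doctor to call an abnormality TB-compatible rather than incidental, so fewer incidental findings are recorded on high-score films.

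The two work in opposite directions and nothing in the planned data would separate them, either from each other or from a real effect of pathology on the software. The count of incidental findings, which is the first half of the endpoint, passes through the same reading. Section 8 applies a two-sided 0.05 threshold to all comparisons, so an artefact of recording could be reported as a significant effect, or a real effect could be masked.

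Who reads the film and in what order is a study procedure set by sections 3 and 6.2. It cannot be repaired afterwards by a choice of analysis on the same recorded findings.

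**Working it through.** The protocol states no effect size, power or expected count for this endpoint, so there is no figure to reproduce. The calculation below only shows what score-dependent recording could do when the true association is nil.

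**Inputs**
- N = 5000: the number to be invited (section 3), used for illustration.
- Share of high-score films = 30%: an assumption. The threshold is not fixed. The Summary expects 20-30% presumptive cases, and the upper end is borrowed as a stand-in.
- True prevalence of incidental findings p = 5%, the same on high- and low-score films (true odds ratio 1): an assumption.
- Probability that a finding is recorded as incidental, s1 on high-score and s0 on low-score films: assumptions.

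**Formula**

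Recorded OR = [s1·p/(1 − s1·p)] / [s0·p/(1 − s0·p)], with z = ln(OR)/√(1/a + 1/b + 1/c + 1/d) from the expected 2×2 counts.

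**Worked case, s1 = 0.90 and s0 = 0.60**
- High-score films: 1500 × 0.05 × 0.90 = 67.5 with a recorded finding, 1432.5 without.
- Low-score films: 3500 × 0.05 × 0.60 = 105 with, 3395 without.
- OR = (67.5 × 3395)/(1432.5 × 105) = 1.52.
- ln(OR) = 0.421, standard error 0.159, z = 2.65, p = 0.008.

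**Other cases, same inputs** (true number of findings 5000 × 0.05 = 250)

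| Recorded, high vs low score | Recorded counts, high + low | OR | p |
|---|---|---|---|
| 90% vs 60% | 67.5 + 105 = 172.5 | 1.52 | 0.008 |
| 90% vs 75% | 67.5 + 131.25 = 198.75 | 1.21 | 0.21 |
| 90% vs 80% | 67.5 + 140 = 207.5 | 1.13 | 0.42 |
| 80% vs 80% | 60 + 140 = 200 | 1.00 | 1.00 |
| 60% vs 80% | 45 + 140 = 185 | 0.74 | 0.09 |
| 40% vs 80% | 30 + 140 = 170 | 0.49 | <0.001 |

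The row with equal recording represents a reading that does not depend on the score. Against its count of 200, the rows with unequal recording lie on both sides (207.5 and 185, for example), so the count can also move either way.

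**Range.** With prevalence varied over 2-10% and the high-score share over 20-30%, still with no true effect:
- 90% vs 60%: OR 1.51-1.55, with a 34-96% chance of p<0.05.
- 90% vs 80%: OR 1.13-1.14, with a 7-22% chance.
- 60% vs 80%: OR 0.73-0.75, with a 13-71% chance.
- Equal recording: OR 1.00, with the nominal 5%.

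**Sensitivity to the number screened.** Section 4.3 cites average consent of 72% among prisoners. With 5000 × 0.72 = 3600 films, the 90% vs 60% case keeps OR 1.52 and its p-value becomes 0.025.

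The endpoint concerns a score from 0 to 100. Splitting it into high and low is a simplification for the illustration; the mechanism does not need a cut-off.

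**The case against.** The strongest case on the other side has several parts.

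- **The reading order is not stated.** Section 3 names both acts in one sentence without requiring the score first, and the case record form, which might fix screen order, is an annex that is not shown. Item 3 does not say it must use the reading made at the visit, and images are stored against the participant number (section 6.3), so a later reading without the score is possible. *What stands:* the bias is not irreversible. But a possible re-reading is not a planned one, and the only X-ray findings variable listed is the doctor's description.
- **Size is unknown.** Prevalence, detection rates and the high-score share are all assumed, and milder differences give unremarkable p-values. *This stands in full.* The illustration shows what could happen, not what will.
- **It is a secondary endpoint.** The doctor cannot change the software score, and sensitivity and specificity are calculated without reference to incidental findings. *This stands*, and it limits the importance of the point.

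A reader might infer more than the protocol supports in three places:
- That the study is bound to find that non-TB pathology raises the score. Relabelling works the other way, and a doctor who ignores the score produces no bias.
- That the introduction singles out score shifts from non-TB pathology as an unresolved question. The issue raised there about incidental detection is one of safety and ethics.
- That the heatmap steers the reading. No passage says the doctor is shown it; the point rests on the score alone.

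**Conclusion.** The concern holds in a limited form. The protocol has the explanatory variable of 6.1.3 item 3 recorded by someone who is given the outcome, and it plans no reading without the score. Detection and labelling can both depend on the score, so the estimated association and the count of incidental findings may be biased upward or downward, and the planned data could not show which.

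The documents fix neither size nor direction. Under declared assumptions (5000 films, 5% prevalence, 30% high scores, no true effect), plausible differences in recording move the odds ratio from about 0.74 (60% vs 80%) to 1.52 (90% vs 60%). A modest difference of 90% vs 75% gives 1.21, which would not reach significance. A real effect of pathology on the score may coexist with the bias. The primary accuracy estimates are not shown to depend on this endpoint. The change is worth making because it is cheap and has to be in place before films are read.

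**What to change.** In section 3 (Visit 1, station 5) and section 6.2, state that:
1. the doctor enters and locks the X-ray description, using the list in 6.1.4 and marking each abnormality as incidental or not, in the electronic case record form before the CAD4TB score (and the heatmap, if it is shown) is displayed;
2. any later change goes in a separate field;
3. only the locked reading is used for 6.1.3 item 3.

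The doctor still sees the score before deciding on health status, so the rest of the visit is unchanged.

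**Cost.** A different screen order, a sentence or two in the protocol, and a slightly longer consultation. No extra reader is needed.

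**Remaining limit.** At station 5 the doctor takes the symptom history first, so a locked reading could still be informed by symptoms, which may correlate with the score through TB. The film should be read before the history where feasible; otherwise the protocol should note this as a limitation.

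**Fallback.** If the screen order cannot be changed, the protocol could specify a reading of the stored images without the score, for all films or a random sample across the score range. This costs reader time.
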